## 8. Potential Risks

### 8.1. Breach of confidentiality

There is minimal risk associated with the collection and recording of patient medical record numbers to permit review of the patient's medical record.

### 8.3 Remote Electrical Neuromodulation with Nerivio ®

Nerivo® is a wearable, remote electrical neuromodulation (REN) device controlled by smartphone application that has been cleared for the acute treatment of migraine in adults and adolescents. Thus, the device is non-invasive and non-pharmaceutical. The device is contraindicated in patients with congestive heart failure, severe cardiac or cerebrovascular disease, or poorly controlled epilepsy and should not be used in patients with active implantable disease such as vagus nerve stimulator (VNS), cardiac pacemaker, deep brain stimulator, or cochlear implant due to theoretical ability to disrupt regular function of the device. It should only be applied to healthy skin that is free of cuts, abrasions, burns, infection, or malignancy. It should not be used near metallic implants. Potential adverse reactions include skin rash or redness under the electrodes of the device.

Patients' skin will be examined for integrity prior to placement of the device. Patients who develop skin rash or redness in response to the study or sham device will be excluded from further investigation.

There is no known risk of Nerivio ® interfering with onabotulinumtoxinA efficacy or administration.

Nerivio ® User Manual will be included in supplemental information separate from this protocol.

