### **3. Preliminary Data**

The utilization of devices for acute procedural pain has been investigated in the past. One such device, the Buzzy®, relies on a vibrating motor and cold sensation to interfere with discomfort related to the procedure. A meta-analysis published in 2018 compiled the results of 9 studies (n=1138) and found that the device significantly reduced self-reported pain levels (standardized mean difference [SMD]: -1.11; 95% confidence interval [CI]: -1.52 to -0.70;  $P < 0.0001$ ), observer-reported pain levels (SMD: -1.19; 95% CI: -1.90 to -0.47;  $P = 0.001$ ), and procedural anxiety (SMD -1.37; 95% CI: -1.77 to -0.96;  $P < 0.00001$ ). The proposed mechanism of action of the Buzzy® device is the Gate Control Theory, whereby non-noxious stimuli interfere with the transmission of painful stimuli at the level of the dorsal horn of the spinal cord (**Ballard, 2018**).

The proposed mechanism of action of Nerivio® differs from the Buzzy® device. Per the device’s manufacturers, Nerivio® produces its effects via remote electrical neuromodulation (REN). REN acts by stimulating peripheral nerves of the upper extremity with electrical stimulus that is not painful. These signals induce a conditioned pain modulation (CPM) response at the level of the brainstem, specifically at the periaqueductal gray and rostral ventromedial medulla (**Yarnitsky, 2019**). Nerivio® has been found to be effective for the acute treatment of migraine headache compared to sham stimulation with significant benefits in pain relief (66.7% [66/99] vs 38.8% [40/103]; therapeutic gain of 27.9% [CI95%, 15.6-40.2];  $P < .0001$ ), pain-free (37.4% vs 18.4%,  $P = .003$ ), and most-bothersome-symptom relief (46.3% vs 22.2%,  $P = .0008$ ) at 2 hours post-treatment. The device also has device-related adverse events (4.8% [6/126] vs 2.4% [3/126],  $P = .499$ ) with the most common adverse events being warmth sensation (2.4% treatment vs 0.8% sham; redness 1.6% treatment vs 0.8% sham; and pain in the arm (1.6% treatment vs 0% sham) (**Yarnitsky, 2019**).

While this device has been studied for acute migraine, further studies are required to determine its effectiveness at treating other types of pain. Of interest to this study, we will be investigating acute procedural pain in the cranial-cervical region.

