#### *7.2.5. Any adverse events.*

#### *7.3. Statistical Analysis*

Subjects will be randomized to treatment vs sham treatment groups utilizing the REDCap. Study data will be collected and managed using REDCap electronic data capture tools hosted at the Mayo Clinic – Arizona. REDCap (Research Electronic Data Capture) is a secure, web-based

CONFIDENTIAL: This document is the intellectual property of [name]. Acceptance of this document constitutes the agreement by the recipient that no unpublished information contained herein will be published or disclosed without prior written approval.

software platform designed to support data capture for research studies, providing 1) an intuitive interface for validated data capture; 2) audit trails for tracking data manipulation and export procedures; 3) automated export procedures for seamless data downloads to common statistical packages; and 4) procedures for data integration and interoperability with external sources (Harris, 2009; Harris 2019).

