### *7.3.2 Statistical Analysis Plan*

Summary statistics will be used to describe the patient population's demographics and clinical characteristics. Patients' pain level change and post-procedure headache after each treatment/sham as well as patients' any adverse events will be summarized in descriptive statistics.

Linear mixed model will be used to analyze the primary outcome for 2 by 2 cross-over study design. Treatment group will be the primary predictor in the model while sequence and period will be adjusted in the model.

Generalized linear mixed model will be used to analyze the effect of treatment on the secondary endpoint presence of post-procedural headache. Similarly, treatment group will be used as the primary predictor while sequence and period will be adjusted in the model.

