### *7.3.3 Interim Analysis Plan*

Interim analyses: One interim analysis will be conducted after 50% of patients have completed the 24 weeks study period. The interim analysis will include the below stopping rule for efficacy and futility based on Lan-DeMets spending function with O'Brien-Fleming boundaries. Occurrence of adverse events will also be evaluated at the interim analysis.

Accrual	Total Number	Efficacy boundary (Z scale)	Alpha spent	Futility boundary (Z scale)	Beta spent
50%	40	+/- 2.96	0.003	+/- 0.35	0.04
100%	80	+/- 1.95	0.05	+/- 1.95	0.2

CONFIDENTIAL: This document is the intellectual property of [name]. Acceptance of this document constitutes the agreement by the recipient that no unpublished information contained herein will be published or disclosed without prior written approval.

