## **9. Management of Intercurrent Events**

### *9.1. Adverse Experiences*

The investigator will closely monitor subjects for evidence of adverse events. All adverse events will be reported and followed until satisfactory resolution. The description of the adverse experience will include the time of onset, duration, intensity, etiology, relationship to the study drug (none, unlikely, possible, probable, highly probable), and any treatment required.

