### *9.2. Premature Discontinuation*

If a subject withdraws from the study, the subject will be replaced to provide the required number of subjects. Subjects will be withdrawn if the investigator decides that discontinuation is in the best interest of the subject, or the subject requests withdrawal from the study. Data collected from patients who withdraw will be kept for analysis however they will not be included in the primary or secondary outcome measures.

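### A week-12 skin reaction leads to removal, and section 9.2 then leaves removed patients out of the adverse-event outcome

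*Combined protocol and SAP*

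**What the plan says.** Five parts of the combined protocol and SAP bear on this point.

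- **Removal.** Section 8.3 (Remote Electrical Neuromodulation with Nerivio): "Patients who develop skin rash or redness in response to the study or sham device will be excluded from further investigation". The same section names rash and redness under the electrodes as the potential adverse reactions.
- **Withdrawal.** Section 9.2 replaces any subject who withdraws. It includes withdrawal decided by the investigator: "Subjects will be withdrawn if the investigator decides that discontinuation is in the best interest of the subject". On analysis it says: "Data collected from patients who withdraw will be kept for analysis however they will not be included in the primary or secondary outcome measures".
- **Outcome.** "Any adverse events" is item 7.2.5 under the secondary outcome measures, and the second of the two secondary outcomes in the synopsis.
- **Analysis.** Section 7.3.2 says "any adverse events will be summarized in descriptive statistics" and names no population. Section 7.3.3 adds: "Occurrence of adverse events will also be evaluated at the interim analysis". It does not say which patients that review covers.
- **Reporting.** Section 9.1: "All adverse events will be reported and followed until satisfactory resolution". Section 10 has the investigators review an annual summary of adverse events, and all serious or unexpected event reports.

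Under section 5.3 a device is first worn at week 12 and the alternative device at week 24.

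**The concern.** Each rule is understandable alone, but together they remove events selectively. A patient with redness at week 12 is taken out because of the redness and replaced. Section 9.2 then leaves that patient out of the secondary outcomes, one of which is the adverse-event outcome. A patient with the same reaction at week 24 has already had every session and would probably count as a completer, so that event is counted. The skin reaction that the protocol expects of the device is therefore the one most open to omission from the device's own safety summary.

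The same sentence in 9.2 also limits the efficacy outcomes. For adverse events there is a further problem: the event being counted is itself the reason for removal. A correction to 9.2 confined to efficacy would leave that in place.

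What is at stake is the completeness of a descriptive safety table, and possibly of the interim safety review.

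**Working it through.** **The plan's own figures.** The plan gives no number for this point. Its 80% power (section 7.3.1) reproduces: noncentrality 0.45 × √(80/2), 78 degrees of freedom, power 0.803, with 0.45 standardised by the within-subject SD. It plays no part below.

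**Reading the sections together**

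1. Adverse events are a secondary outcome (synopsis; 7.2.5).
2. Withdrawn patients are not in the secondary outcomes (9.2), and adverse events are not exempted.
3. Rash or redness on either device ends participation (8.3). The text does not call this withdrawal. Section 9.2 does cover discontinuation in the patient's interest, and no other section says how an 8.3 removal is analysed.
4. Sections 7.3.2, 7.3.3, 9.1 and 10 neither define a safety population nor override 9.2.

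On that reading, week-12 reactors leave the adverse-event outcome.

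**Inputs for the size**

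- 80 patients, 40 per sequence (7.3.1), so 40 active and 40 sham sessions at week 12.
- Section 3 gives "redness 1.6% treatment vs 0.8% sham" in the earlier sham-controlled trial of the device in acute migraine. Device-related events of any kind there were 4.8% (6/126) and 2.4% (3/126).
- Assumption: those rates apply to each session here.

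**Expected week-12 redness**

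- Active: 40 × 0.016 = 0.64
- Sham: 40 × 0.008 = 0.32
- Total: 0.96
- Chance of at least one: 1 − 0.984^40 × 0.992^40 = 0.62

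**Share of all device-related events over both visits**

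- 80 × 0.048 + 80 × 0.024 = 3.84 + 1.92 = 5.76
- 0.96 / 5.76 = one sixth

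**Reported redness rate, with week-12 reactors replaced and week-24 reactors kept**

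- Active: (0 + 40 × 0.016)/80 = 0.8%, against 1.6%
- Sham: (0 + 40 × 0.008)/80 = 0.4%, against 0.8%
- In general: (0 + 40p)/80 = p/2

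The denominator stays at 80 sessions per device; only the numerator loses its week-12 events. The halving needs the per-session risk to be similar at the two visits, but it does not depend on the value of p. The absolute difference between devices halves too, from 0.8 to 0.4 percentage points.

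**Range.** With 126 patients per arm, the cited percentages correspond to 2/126 and 1/126, pooled 3/252. The exact 95% interval is 0.25% to 3.44%. Over the 80 week-12 sessions:

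| Pooled rate | Expected cases | Chance of at least one, 1 − (1 − p)^80 |
|---|---|---|
| 0.25% | 0.20 | 18% |
| 3.44% | 2.75 | 94% |

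**The case against.** The strongest reply is that the link between the two sections is inferred. Section 8.3 does not use the word withdrawal. Section 9.2 names two routes, the investigator's judgement of the patient's interest and the patient's request, and an automatic stop for a skin reaction is not listed as a third. The wording of 8.3 also looks forward: it could mean no more device sessions and say nothing about data already collected. Other text favours counting the event. Section 9.1 covers all adverse events, 7.3.2 has no completer restriction, and 9.2 itself keeps the data.

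This has force, and the link remains an inference. It does not close the gap. Reporting and following an event is different from tabulating it as an outcome, and 9.2 itself separates keeping data from including them in the outcomes. It is the only text that says who is left out of the secondary outcomes.

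The second reply is size: about one expected case, a 38% chance of none, a listed reaction to a cleared device, and a descriptive table. That is correct, and it limits the importance of the point. Warmth and arm pain, also reported in the earlier trial, do not trigger removal under 8.3.

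The third is that this is part of a wider problem with one sentence in 9.2. The root is shared, and the corrections can be made together. Adverse events still need their own population, based on the device worn, which a change to the efficacy analysis would not supply.

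**Conclusion.** The concern holds. Section 9.2 has no exemption for adverse events, adverse events are a secondary outcome, and no safety population is defined. Taken with 8.3, the plan can drop a week-12 skin reaction from the adverse-event outcome because that reaction occurred.

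The expected number affected is 0.96 (range 0.20 to 2.75), and reported redness would be about half the true rate on each device. This rests on three assumptions: that an 8.3 removal is a 9.2 withdrawal, that week-24 reactors count as completers, and that per-session rates match those cited from acute migraine use. The event stays in the records, and the primary estimate, power and type I error are untouched. It should be fixed because the omission is selective and the correction is simple.

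**What to change.** - **Section 9.2:** exempt the adverse-event outcome from the exclusion of withdrawn patients.
- **Section 7.3.2:** state that adverse events, at both the interim and final analyses, are summarised for every patient who had an active or sham device applied, by device worn, whether or not the patient completed or was replaced. Report the number removed for a skin reaction, by device.
- **Section 8.3 (Nerivio):** state that removal for rash or redness means no further device sessions, with the next-day contact and follow-up to resolution kept.

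The cost is one sentence in each section, and they can go in with any other correction to 9.2. No new data are needed: 9.1 already collects the events and 9.2 already keeps withdrawn patients' data. The reported reaction rate may look slightly less favourable to the device.

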### 8.2. OnabotulinumtoxinA administration

OnabotulinumtoxinA is a product of Allergan Pharmaceuticals (BOTOX ®, Abbvie, North Chicago, IL). Botulinum toxin is a neurotoxin produced by the bacterium *Clostridium botulinum*. The mechanism of action of botulinum toxin is the inhibition of acetylcholine release at the neuromuscular junction by binding to SNARE (SNAP Receptor) proteins at the synaptic bouton. The pharmacologic mechanism of botulinum toxin prevents the build-up of intracellular sodium ions and subsequent generation of the endplate potential required for calcium channel activation that induces muscle contraction. Botulinum toxin is potentially fatal when absorbed systemically, typically via infection with *Clostridium botulinum* spores (i.e., botulism) or exposure to large amounts of foodborne toxin.

While the mechanism of action of botulinum toxin through inhibition of acetylcholine release at the neuromuscular junction is a sufficient explanation for its effects at reducing spasticity, it is a matter of debate how local, intramuscular injection of the toxin reduces headache frequency and intensity in patients with chronic migraine. Proposed mechanisms involve local uptake and inhibition of proteins known to be involved in migraine pathophysiology such as calcitonin gene-related peptide (**Burstein, 2020**). While further research is required to elucidate its mechanism, onabotulinumtoxinA has been found to be effective at reducing headache burden when applied via the PREEMPT protocol, which involves the injection of 5U into 31 injection sites (total 155U) with the option for additional injections (up to 40U) based on a follow-the-pain strategy and must be administered every 10 to 12 weeks to maintain effect (**Aurora, 2010; Diener, 2010**). In usual clinical practice, patients will receive between 150 and 200U based on vial size made available

CONFIDENTIAL: This document is the intellectual property of [name]. Acceptance of this document constitutes the agreement by the recipient that no unpublished information contained herein will be published or disclosed without prior written approval.

by the pharmaceutical company with most patients receiving between 155 and 200U every 10 to 12 weeks.

The risks involved with local onabotulinumtoxinA for the treatment of chronic migraine include temporary increased neck pain, headache, bruising, bleeding, and infection at the injection site. There is a low risk of brow ptosis following administration of onabotulinumtoxinA to the forehead that is temporary. Patients are also informed that there is a Boxed Warning applied to onabotulinumtoxinA regarding the Distant Spread of Toxin Effect that can be life-threatening and involve symptoms similar to systemic absorption of the toxin, namely swallowing and breathing difficulties. Generally, the risk of life-threatening adverse effect is exceedingly rare and is highest in patients receiving the toxin for treatment of spasticity (higher unit amount injected) and in children (BOTOX full prescribing information).

### *8.3 Steps Taken to Mitigate Risk*

Studies are conducted under the supervision of the investigating physicians who are trained and experienced in performing research in human subjects.

Inclusion and exclusion criteria, monitoring, and the clinical protocol are designed to ensure that risks are minimal. Subjects are informed that participation is voluntary, and they may refuse to participate and may withdraw from the study at any time without penalty.

With regard to confidentiality: (1) all subjects will be assigned a study ID number, (2) the link to identifiers will be deleted at the end of the study, (3) data will be stored in REDcap. If data are published, there will be no link to identifiers. Study data will not be revealed to any organization, individuals other than the subjects, or the subjects themselves, (4) study data will not be entered in subjects' medical records.

## **9. Management of Intercurrent Events**

### *9.1. Adverse Experiences*

The investigator will closely monitor subjects for evidence of adverse events. All adverse events will be reported and followed until satisfactory resolution. The description of the adverse experience will include the time of onset, duration, intensity, etiology, relationship to the study drug (none, unlikely, possible, probable, highly probable), and any treatment required.

### *9.2. Premature Discontinuation*

If a subject withdraws from the study, the subject will be replaced to provide the required number of subjects. Subjects will be withdrawn if the investigator decides that discontinuation is in the best interest of the subject, or the subject requests withdrawal from the study. Data collected from patients who withdraw will be kept for analysis however they will not be included in the primary or secondary outcome measures.

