## 1. Background and Rationale:

Migraine is a condition that impacts a large segment of the global population (~958.8 million) and is exceeded only by stroke with regards to its overall burden of neurological disease (**GBD 2015 Neurological Disorders Collaborator Group**). It has been estimated that the prevalence of total migraine (episodic and chronic) is about 20.7% in women and 10.7% in men in the United States (**Burch 2020**). Of the patients with episodic migraine, it has been shown that around 2.5% will progress or “transform” into chronic migraine, defined as headache that occurs  $\geq 15$  days per month with at least 8 headaches with features of migraine based on the International Classification of Headache Disorders 3rd Edition (ICHD-3) criteria (**Buse 2012, see ICHD-3 criteria in supplemental material**).

The injection of onabotulinumtoxinA (BoNT-A) is common treatment for patients with a wide variety of conditions such as chronic migraine, cervical dystonia, spasticity, strabismus, neurogenic bladder, and hyperhidrosis. Proper implementation of this treatment modality can involve the injection of BoNT-A into many different sites per procedural visit and must be repeated to ensure continued effect. BoNT-A for the treatment of chronic migraine is administered per PREEMPT protocol, which involves the injection of 5U into 31 injection sites (total 155U) with the option for additional injections (up to 40-45U) based on a follow-the-pain strategy and must be administered every 10 to 12 weeks to maintain effect (**Aurora, 2010; Diener, 2010**). While levels of procedural discomfort do not appear to predict therapy continuation (**Anderson, 2020**), steps should be taken to reduce needle-related pain to minimize stress and anxiety surrounding the procedure.

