**5.3. Treatment Phase**

Upon receipt of informed consent, the patient will enter phase 1 of the study. This phase is used to determine baseline experience with the PREEMPT protocol and will involve obtaining pre-, intra-, and post-procedural pain intensity levels based on a standard visual analog scale. Subjects will then be contacted the following day to inquire about the presence of post-procedural headache. Following their initial treatment of BoNT-A, subjects will then be randomized to receive either remote electrical neuromodulation with Nerivio® or stimulation with a sham device for their next BoNT-A treatment and enter phase 2. During phase 2, patients will again receive BoNT-A treatment via PREEMPT protocol at week 12 +/- 7 days (buffer period to accommodate rescheduling) and will also be treated with either Nerivio® or receive stimulation with a sham device supplied by **Theranica Bio-electronics, Ltd.** Patients will have the device applied 20 minutes prior to starting the Botox procedure with an estimated total time of wearing the device around 40 to 45 minutes. Again, patients will be surveyed regarding their pre-, intra-, and post-procedural pain intensity and will be contacted on the following day re: post-procedural headache. Finally, patients will receive their final treatment of BoNT-A at week 24 +/- 7 days and will receive concurrent treatment with the alternative stimulation setting (either Nerivio® treatment stimulation or sham stimulation). Pre-, intra-, and post-procedural pain levels and post-procedural headache will be recorded in an identical fashion.

CONFIDENTIAL: This document is the intellectual property of [name]. Acceptance of this document constitutes the agreement by the recipient that no unpublished information contained herein will be published or disclosed without prior written approval.

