### *7.3.1 Sample Size Consideration*

Primary endpoint: Pain level change from pre-treatment/pre-sham, intra-treatment/intra-sham, and post-treatment/post-sham

A two-sided t-test achieves 80% to infer that the mean difference (between treatment and sham) is not 0 when the total sample size of a 2x2 cross-over design is 80 with an equal number in each sequence (n=40/sequence) when the actual effect size is 0.45 (standardized difference, medium effect size) and the significance level is 0.05.

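### Section 9.2 drops withdrawn patients' phase 2 data from the pain and headache comparisons, although those data are kept and the planned mixed models can use them

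*Combined protocol and SAP*

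**What the plan says.** Section 9.2 (Premature Discontinuation) has two rules. On numbers: "If a subject withdraws from the study, the subject will be replaced to provide the required number of subjects". On data: "Data collected from patients who withdraw will be kept for analysis however they will not be included in the primary or secondary outcome measures". Withdrawal may be at the investigator's decision or the patient's request, and no exception is made for patients already randomised or measured.

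Section 5.3 fixes the order of events: "Following their initial treatment of BoNT-A, subjects will then be randomized to receive either remote electrical neuromodulation". Phase 2 follows at week 12 and phase 3, with the other device setting, at week 24. Every phase 2 measurement is therefore post-randomisation, and about 12 weeks remain in which to withdraw.

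Section 7.3.2 names the analyses: "Linear mixed model will be used to analyze the primary outcome for 2 by 2 cross-over study design", and "Generalized linear mixed model will be used to analyze the effect of treatment on the secondary endpoint presence of post-procedural headache". Both adjust for sequence and period. The section defines no analysis set and no missing-data rule. Section 7.3.3 adds: "One interim analysis will be conducted after 50% of patients have completed the 24 weeks study period".

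**The concern.** A patient who withdraws between weeks 12 and 24 has a pain score and a headache report under a randomly assigned device. Section 9.2 keeps these data and then bars them from every outcome they could inform. The restriction comes from section 9.2 alone, since a mixed model with a patient effect accepts a patient with one period.

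What is at stake is selection, not numbers. Replacement brings the count back to 80, but the patients analysed have been selected on something that happened after randomisation. If withdrawal depends on phase 2 pain, those who remain have phase 2 scores that are too low, and this enters the device-sham difference with opposite signs in the two sequences. It cancels only if the selection is equally strong in both.

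**Working it through.** **1. The plan's own figure.** Section 7.3.1 gives N = 80 (40 per sequence), effect size 0.45, two-sided alpha 0.05 and 80% power. Read 0.45 as the difference divided by the within-subject SD. Then SE = sqrt(2/80) = 0.158, the non-centrality is 0.45/0.158 = 2.846, df = 78, and power is 0.803. The figure is reproduced. (Dividing by the SD of paired differences would give 0.978, which does not match.) Effects below are in within-subject SDs.

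**2. Assumptions.** The protocol gives no withdrawal rate, no reasons and no correlation between periods. I assume:
- pain = patient effect + treatment effect + residual with SD 1;
- intraclass correlation r from 0.3 to 0.7;
- true effect -0.45;
- patients with phase 2 pain above the 90th or 80th percentile withdraw (q = 10% or 20%);
- replacement up to 40 completers in each sequence (section 9.2 does not say which sequence a replacement joins).

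**3. Bias when withdrawn patients are dropped.** Total variance is 1/(1 - r). Removing the top fraction q on phase 2 pain lowers the mean phase 2 residual of those who remain by

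D = sqrt(1 - r) × phi(z_q)/(1 - q),

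where phi(z_q)/(1 - q) is 0.195 for q = 10% and 0.350 for q = 20%. The patient effect cancels within patient, and the estimate averages the active-minus-sham difference over the two sequences. The bias is therefore -D/2 if only active-first patients leave, +D/2 if only sham-first patients leave, and (D_sham-first - D_active-first)/2 if both do.

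Example, one sequence, r = 0.3, q = 20%: D = 0.837 × 0.350 = 0.293, so the bias is ±0.146.

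Example, same cut-off in both, r = 0.5, q = 20% of sham-first: the cut-off is 0.842 SD above the sham mean and 0.842 + 0.45 × 0.707 = 1.160 SD above the active mean, so 12.3% of active-first leave. The values of D are 0.247 and 0.164, the bias is +0.042, and the estimate is -0.408.

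| r | q | D/2 | Active-first only | Sham-first only | Same cut-off in both |
|---|---|---|---|---|---|
| 0.3 | 10% | 0.082 | -0.53 | -0.37 | -0.41 |
| 0.3 | 20% | 0.146 | -0.60 | -0.30 | -0.39 |
| 0.5 | 10% | 0.069 | -0.52 | -0.38 | -0.42 |
| 0.5 | 20% | 0.124 | -0.57 | -0.33 | -0.41 |
| 0.7 | 10% | 0.053 | -0.50 | -0.40 | -0.43 |
| 0.7 | 20% | 0.096 | -0.55 | -0.35 | -0.42 |

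Simulation with 20,000 trials per setting agrees to within about 0.003. Power is 75-79% with the same cut-off in both sequences and 51-71% with sham-first loss only. Random loss gives -0.45 and 80%.

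**4. False-positive rate with no true effect.**
- Same cut-off in both sequences: the two values of D are equal, the bias is zero and the rate is about 5%.
- All high-pain patients leave one sequence and none the other: at r = 0.3, q = 20%, bias/SE = 0.146/0.158 = 0.93, which gives about 15%. Simulation gives 6-16% across settings.
- Half leave one sequence and none the other: 5-7%.
- All leave one sequence and half the other: about 5-8%. Half and a quarter: about 5-6%.

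Applying the two looks of section 7.3.3 (2.96 with futility 0.35, then 1.95) leaves the two ranges for loss from one sequence only at 6-16% and 5-7%.

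**5. All randomised patients with data, replacements added.** When withdrawal depends on phase 2 pain or is random, the estimate is -0.446 to -0.453 and the false-positive rate 4.6-5.3%. This simulation took the variance components as known, whereas the planned model must estimate them. Nothing was computed for the headache model.

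**6. Where the fix does not help.** If withdrawal depends on phase 3 pain that is never observed, both analyses are biased. Loss from both sequences gives -0.39 to -0.43 without withdrawn patients and -0.38 to -0.42 with them. One-sequence false-positive rates are 6-16% and 9-22%.

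**The case against.** **Scope.** A reader might infer that the plan prescribes a completers-only analysis. It does not. Section 9.2 covers patients who withdraw. A patient who misses phase 3 or is lost to follow-up without withdrawing is not mentioned, and section 7.3.2 sets no completer restriction. This objection stands, and the point is confined to withdrawn patients.

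**Weight.** A reader might take 16% as the expected false-positive rate. It requires every high-pain patient in one sequence to leave and none in the other. With no true effect, phase 2 pain has the same distribution in both sequences and the trial is single-blind, so pain alone would prompt equal leaving. The only device-linked exit described is exclusion for rash or redness (section 8.3 on the device), which is not driven by pain. The background section also reports that "levels of procedural discomfort do not appear to predict therapy continuation". That concerns staying on therapy rather than in the study, so it makes strongly pain-related withdrawal less likely without excluding it. This objection stands as to size; it does not justify discarding the data.

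**The remedy is not uniformly better.** Under withdrawal driven by unobserved phase 3 pain, including everyone does somewhat worse (step 6). This stands, and it is why the fix needs a sensitivity analysis for that case.

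**Adverse events.** These are a listed secondary outcome, so a reader might infer that withdrawn patients' events would go unreported. Section 9.1 requires all adverse events to be reported, and the summary in section 7.3.2 has no completer limit. Only the wording conflicts. At the redness rates in section 3, assumed to carry over from acute migraine treatment, 40 × 0.016 + 40 × 0.008 = 0.64 + 0.32 = 0.96 phase 2 cases are affected.

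**Conclusion.** The point holds for randomised patients who are measured in phase 2 and withdraw before phase 3. Section 9.2 removes them from the pain and headache comparisons and replaces them, and no other section brings them back.

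Neither the size nor the direction of the bias can be derived from the protocol. Under the stated assumptions it is nil for random withdrawal and at most about 0.06 SD towards no effect when one pain cut-off applies in both sequences. It reaches about 0.15 SD in either direction only when withdrawal is wholly one-sided. The documents do not support a claim that the trial would favour the device or that its error rate is materially inflated. The change is worth making because the rule discards usable randomised data and correcting it costs little.

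**What to change.** Replace the last sentence of section 9.2 with the following:

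1. The primary and headache mixed models include every randomised patient with at least one phase 2 or phase 3 measurement, by assigned sequence, whether or not the patient later withdraws. Replacements are added and do not displace the patients they replace.
2. The main model assumes that leaving depends only on observed data. The analysis without withdrawn patients is a sensitivity analysis, and a simple sensitivity analysis for departures from that assumption is added, for example shifting the unobserved phase 3 values over a range.
3. Withdrawals after randomisation are reported by sequence and timing, and by reason where recorded.
4. At the interim look, patients who have completed 24 weeks and those who withdrew after a phase 2 measurement are included; patients still awaiting phase 3 are not. The timing and boundaries in section 7.3.3 stay as written.

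Footnote on wording: state that the adverse-event summary in section 7.3.2 covers all enrolled patients regardless of withdrawal, by phase and by the device most recently applied (the device is worn for only about 40 to 45 minutes, so many events may start after removal), with phase 1 events shown separately. Reconcile section 9.2 with the device-risk section on whether exclusion for rash or redness counts as withdrawal for data handling. The clinical exclusion itself is not questioned.

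Cost: one paragraph. The outcome data are already kept, and no patients are needed beyond the replacements already planned. The downside is explicit reliance on a missing-at-random assumption and a little more analysis work.
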